We propose a prospective, open-label, single-arm pilot study treating 40 subjects to assess the hypothesis that P2Y12 inhibition with Brilinta/ticagrelor (90 mg PO twice a day) reduces episodic and/or chronic migraine headache symptoms in patients with right to left shunt. There will be no randomization or blinding of therapy. The study drug will be provided, free of charge, by the manufacturer, Astra-Zeneca. All subjects will be treated with the same medical regimen, and will be treated at Columbia University Medical Center or one of Principal Investigators external offices. All subjects will have an initial visit that will include the completion of a screening questionnaire (inclusion/exclusion criteria), informed consent, transcranial Doppler screening, laboratory blood testing by venipuncture (approximately 15 cc of blood = 1 tablespoon), and instruction on the use of the daily headache log (see Appendix 1, Appendix 2). Over the next 28 days, the subjects will receive an e-mail/text reminder daily with a link to complete the headache log (see below). At a second study visit, following completion of the first baseline month, the study staff will review the subject's headache log material, will release those subjects with insufficient headache days in the screening month, will assign the remaining/eligible subjects to either the episodic or chronic migraine cohort, will distribute the study drug, will administer the Brilinta/ticagrelor loading dose, and will review the medication's proper use. After 7 days of treatment with Brilinta/ticagrelor, while still on therapy, subjects will be sent for additional laboratory testing (PRU test < 10 cc of blood by venipuncture). At the completion of the 28 days (+7 days) on Brilinta/ticagrelor, each subject will have a follow-up study visit within 7 days, before discontinuing medication. At the third study visit, headache logs will be reviewed with the study staff, results will be discussed, remaining medications and empty bottles will be returned, and adverse events will be reviewed. Headache frequency while on Brilinta/ticagrelor will be compared with the documented baseline for each subject. If the Brilinta/ticagrelor therapy was effective (> 50% reduction in monthly headache days), the subject could elect to continue therapy for an additional two months, while continuing to complete daily headache logs.

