Baseline-Monitoring Phase (Phase 1): The subject will track her/his headaches daily for 28 days through an online survey tool (REDCap, licensed through Columbia University), to establish a baseline headache frequency. Each day, the subject will receive a text message/e-mail reminder to complete the daily headache log. The message will contain a link to log into the survey tool. During this phase, subjects will answer questions including presence or absence of headache symptoms, severity of headache symptoms, duration of symptoms, impact on daily activities, and use of rescue medication. Any headache lasting more than 24 hours will be counted as a second headache day. After 28 days of monitoring, the study coordinator will assess the subject's data to make sure the subject meets criteria for minimum headache days, and has been consistently performing the daily log. If the number of headache days is insufficient, the subject's participation will be completed. If the subject logs at least 6 headache days in the month, she/he will continue in the study. If the participant has been assigned to the Episodic arm of the study, but has >14 headache days in the screening month, or if the participant has been assigned to the Chronic arm of the study, but has <15 headache days in the screening month, she/he will NOT be reassigned, but will remain in the assigned group for analysis. The subject will then be treated with Brilinta/ticagrelor for a 28-35 day test period (Phase 2). The length of the test period will depend on the timing of the participant's follow-up visit after beginning treatment. The protocol window is 28+7 days.

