Treatment Phase (Phase 2): The subject will return for a follow-up visit to receive her/his medication within 1 week of completing the 28 day headache log. A loading dose of Brilinta/ticagrelor 180 mg will be administered in the office. Thereafter, for 28-35 days, a Brilinta/ticagrelor 90 mg tablet will be taken once in the morning and once in the evening, as close to 12 hours apart as possible. Each day, the subject will receive a text message reminder to login to the website, to record her/his headache activity. If she/he fails to login for two consecutive days, the study coordinator will place a follow-up phone call. PRU testing will be done a minimum of 7 days after the initiation of treatment, but before the medication is completed. A follow-up visit will be arranged between day 28 and day 35 days of monitoring to review efficacy, compliance, and side effects, to return unused medication, and to allow continued access to Brilinta/ticagrelor if indicated. A second Quality of Life survey will be completed.

Continued Access Phase (Phase 3): If the subject has a beneficial response to the Brilinta/ticagrelor (> 50% reduction in the average number of monthly headache days compared with the baseline), she/he will be offered continued access to the medication to complete an additional 2 months of therapy with on-going headache monitoring. A final office visit and Quality of Life Survey will be completed within 7 days of the 56th day of Phase 3 for return of unused medication, empty medication bottles and discussion about future therapeutic options. If the subject fails to have a beneficial response following the first month of treatment (Phase 2), the medication will be discontinued and participation in the study will be completed. If the subject elects to discontinue the Brilinta/ticagrelor, despite a beneficial response, participation in the study will be completed.

Outcomes Assessment/Statistical Analysis

Information from this study will be assessed to determine the feasibility of performing a larger randomized, blinded, placebo-controlled multi-center trial. We will assess not only our therapeutic drug response rate in order to estimate a required sample size for the future trial, but also our ability to recruit patients from local referring sources to estimate the time frame of such a trial. Subject compliance rate with use of daily online questionnaires will be determined. Drop-out rates, related to medication side effects will also be assessed.

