1. Statistical Considerations and Analysis Plan:

This is a prospective, open label single-armed trial designed to evaluate the safety and efficacy of Brilinta/ticagrelor (90 mg twice daily) used off-label, in a young healthy population, for the treatment refractory migraine headache. The primary endpoints are:

- Efficacy – Response to treatment defined as a $\geq 50\%$ reduction in chronic headache during a three month period of therapy, compared with baseline.
- Safety – Bleeding events and adverse medication reactions measured over the 3 month treatment period.

Only 40 subjects will be treated in this initial feasibility trial, 20 with episodic migraine, 20 with chronic migraine. We will assess the number of “Responders” in each study group. Responsiveness will be compared with the measured PRU while on therapy. The results of this trial will be descriptive only. It is not anticipated that the number of subjects enrolled will provide statistically analyzable results.

However, if treatment were to be seemingly beneficial, these data could form the foundation for the development of a pivotal randomized, blinded, prospective trial in a larger cohort as mentioned above.

The safety analysis set will include all subjects who receive at least one dose of study medication. This will be the primary analysis set for all safety endpoints which will include major bleeding complications, and adverse drug reactions. Bleeding outcomes, in this younger, healthier cohort will be compared with the previously published PLATO Trial²¹.

Any participant who completes her/his daily headache logs for at least two weeks, but not the full month of the study period, will be classified according to her/his current response status (LOCF), regardless of whether or not he/she completed the required therapy.

2. Analysis of Secondary Endpoints

The secondary endpoints, which will be reported, are as follows:

- Absolute reduction in headache days as a continuous response variable.
- Comparison of the use of rescue medications in the roll-in versus the treatment phase and “successful” interruption of MHA (< 2 hours to resolution) with rescue therapy.
- Non-major bleeding side effects of the medication

STUDY PROCEDURES:

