(28-35 Days) Participant will receive reminder text message/e-mail to take daily study medication, and to log-in to answer the headache log questions. Participant will take Brilinta/ticagrelor 90 mg twice daily for 28-35 days. Participant will receive instructions for PRU testing.

PRU Testing: (> 7 days on drug)	Participant will go to local laboratory or to study center for blood testing of platelet inhibition.
Study Visit #3:	Within 7 days of completion the 28 th day of the study medication participant will return to meet with the study coordinator to review the results of the therapy, to return unused medication, and to review any adverse events. If no perceived benefit, participation is completed. If subject has had a clinical benefit, options for on-going therapy with additional headache log entries will be discussed. Participant will complete a follow-up Quality of Life questionnaire.
Continued Access (56-63 days):	If eligible, participant will continue to take Brilinta/ticagrelor for an additional 2 months. She/he will continue to receive daily e-mail/text message reminders to log-in to record headache data.
Study Visit #4:	Within 7 days of the 56 th day of study medication, participant will return to meet with the study coordinator to review the results of the therapy, to return unused medication, and to review any adverse events. Participant will complete a follow-up Quality of life questionnaire. Study is complete.

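### Continued access yields 56-63 further days of headache logs from subjects selected on month 1, but no stated analysis reports those days apart from that month

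*Combined protocol and SAP*

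**What the plan says.** All references are to the combined protocol and SAP.

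- **Entry to Phase 3.** Under Continued Access Phase (Phase 3), a subject with more than a 50% reduction from baseline in the first treatment month is eligible: "she/he will be offered continued access to the medication to complete an additional 2 months of therapy with on-going headache monitoring". Continuation is elective. Subjects without that response stop drug and leave the study.
- **Data.** Appendix 1 sets the period at 56-63 days and keeps the daily log running: "She/he will continue to receive daily e-mail/text message reminders to log-in to record headache data". Appendix 2 agrees.
- **Primary endpoint, one month.** Primary Study Endpoints defines a Responder by a reduction of at least 50% in the single month of therapy.
- **Primary endpoint, three months.** Statistical Considerations and Analysis Plan asks for the same 50% as a "reduction in chronic headache during a three month period of therapy, compared with baseline".
- **Secondary endpoints.** Absolute reduction in headache days has no period attached. Rescue use is compared between roll-in and treatment phase. Neither list of secondary endpoints names Phase 3. The quality-of-life survey is repeated after Phase 3, but no analysis of it is stated.
- **Status of the results.** "The results of this trial will be descriptive only".

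**The concern.** Phase 3 subjects are there because month 1 was low relative to their baseline. Month 1 therefore overstates their improvement, whether or not the drug works. The Phase 3 logs are on-drug data from the same people that played no part in selecting them. As written, the plan either leaves these logs out (one-month wording) or averages them with the selecting month (three-month wording). The second route carries the month-1 selection into the reported reduction. It also cannot be computed for all 40 subjects, because those without the qualifying response have no second or third month.

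This matters because Outcomes Assessment/Statistical Analysis says the observed response rate will be used to size the future randomized trial. How far the month-1 response holds up is useful for that purpose, and the data to describe it are already being collected.

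**Working it through.** **The plan's own figures.** No figure in the plan bears on this point. The only derived number is the screening target, 40 / 0.25 = 160. It reproduces, and nothing here depends on it.

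**Inputs from the documents.** Single arm: "There will be no randomization or blinding of therapy". Cohorts: "Only 40 subjects will be treated in this initial feasibility trial, 20 with episodic migraine, 20 with chronic migraine". Baseline: "The subject will track her/his headaches daily for 28 days through an online survey tool". Threshold to continue: "If the subject logs at least 6 headache days in the month, she/he will continue in the study". Entry to Phase 3 requires a month-1 reduction above 50%.

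**Assumed inputs (not in the documents).** Episodic long-run rate with mean 9 headache days per 28 and SD 2.5. Month-to-month variation from pure binomial to beta-binomial with concentration 15. Each month is 28 days. Two scenarios: no drug effect, and a 70% cut in 60% of subjects.

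**Formulas.** Let b be baseline days, m1 month-1 days, and m2 and m3 the two Phase 3 months.

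- Entry: m1 < b/2
- Month-1 reduction: R1 = 1 − m1/b
- Phase 3 reduction: R3 = 1 − (m2 + m3)/(2b)
- Pooled reduction: 1 − (m1 + m2 + m3)/(3b) = (R1 + 2·R3)/3

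**Results, episodic (binomial to concentration 15).**

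| | No drug effect | 70% cut in 60% |
|---|---|---|
| Enter Phase 3 | 5-18% | 52-55% |
| Entrants' mean reduction, month 1 | 63-69% | 76-81% |
| Entrants' mean reduction, Phase 3 alone | 24-26% | 67-70% |
| Entrants keeping ≥50%, pooled | 22-39% | 87-95% |
| Entrants keeping ≥50%, Phase 3 alone | 14-28% | 81-92% |

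Entrants' pooled mean reduction with no drug effect follows from the formula: (63 + 2×24)/3 = 37% and (69 + 2×26)/3 = 40%.

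**Sensitivity.** A second assumed set used long-run rates uniform on 4-14 days and intra-subject monthly correlation 0 to 0.15. With no drug effect, episodic entrants' mean reduction was 64-75% in month 1, 39-45% pooled and 26-30% in Phase 3. The pattern is the same. For chronic subjects (rates uniform on 15-26 days) it was 56-64%, 29-30% and 13-16%.

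**Expected counts with no drug effect.** Episodic: 20 × 0.05 = 1 to 20 × 0.18 = 3.6, so about 1-4 entrants. The second set allows 5-31%, or about 1-6. Chronic: 0.1-7% reach a 50% reduction in month 1, so 20 × 0.07 = 1.4 at most, about 0-1. Exact 95% intervals at such counts are very wide: 0 of 2 kept gives 0-84%, and 1 of 4 gives 1-81%.

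**What the Phase 3 comparison still carries.** Entry depends on m1 relative to b, so it also picks baselines that are high by chance. With no drug effect, entrants' observed baseline is 10.5-12.4 days against true means of 7.8-8.6. As ratios of means, 1 − 7.8/10.5 = 26% and 1 − 8.6/12.4 = 31%, close to the 24-26% average of individual reductions. The reduction left in Phase 3 is a baseline artefact.

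**The case against.** The strongest reply is that little is lost. The trial is declared descriptive, the logs will exist, and the secondary endpoint on absolute reduction names no period, so Phase 3 could be tabulated at reporting. That is correct: the gap is in the stated analysis, not in the data. But a window chosen after the data are seen invites selective reporting.

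Three stronger readings should be resisted.

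- **That month 1 alone cannot tell an ineffective drug from an effective one.** The documents give no variability figures to support this. Under the assumed inputs the month-1 count already separates the scenarios: 5-18% against 52-55% entering, or about 1-4 against 10-11 of 20.
- **That pooling destroys the contrast.** For the share keeping at least 50%, the gap between scenarios is 92 − 14 = 78 points in Phase 3 alone against 95 − 22 = 73 pooled (binomial), and 81 − 28 = 53 against 87 − 39 = 48 (concentration 15). Leaving month 1 out gains only about 4-5 points. What pooling does distort is the size of the reduction reported for entrants.
- **That Phase 3 is the best internal check available, or that persistence would show the drug works.** With no control arm or blinding, a lasting placebo response looks the same as a lasting drug effect. Selection on the baseline month and elective continuation also remain.

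It is also fair to say that this is mainly an episodic-cohort issue, since few chronic subjects would reach a 50% reduction by chance.

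**Conclusion.** The point holds in a limited form. Continued-access logs come from subjects chosen on a month-1 reduction above 50%, and no stated analysis reports them apart from that month. The three-month wording inflates the apparent reduction in entrants: with no drug effect, to 37-40% against 24-26% in Phase 3 alone, a difference of about 13-14 points in the illustrative episodic simulation. Those percentages rest on assumed rates and month-to-month variation and show direction and range only.

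The clearest error in the text is the conflict between the one-month and three-month primary endpoints. The missing Phase 3 summary is a cheap improvement beside it and does not invalidate the month-1 result.

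**What to change.** 1. Reconcile the one-month wording in Primary Study Endpoints with the three-month wording in Statistical Considerations and Analysis Plan, and say which logs each analysis uses.
2. Add a descriptive secondary endpoint on Phase 3 logs only, under Analysis of Secondary Endpoints. Among month-1 Responders, by cohort, report for Phase 3 days 1-28 and 29-56 the number keeping at least a 50% reduction from baseline, with exact intervals, and the mean change in headache days per 28 with its interval. Exclude month 1.
3. Count Responders who decline or stop Phase 3 as not shown to be maintained, and list them separately.
4. List separately Responders at exactly 50%. The Responder definition includes them, but the Phase 3 offer requires more than 50%, so they have no later logs (about 3% of episodic subjects in the no-effect simulation). The two thresholds must be reconciled.
5. State the limits beside the table: persistence, not drug effect; baseline selection, elective continuation and lasting placebo response remain; counts are small and intervals wide.

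The cost is one extra table, with no new visit or measurement. The headline benefit may look smaller.

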Appendix 2:

TRACTOR Migraine Flow Chart: Events and responsibilities are described for each phase of the trial.

Events	Study Visit #1	Phase 1 (28 Days)	Day 29	Study Visit #2	Phase 2 (28-35 Days)	PRU visit	Study Visit #3	Continued Access (56-63 Days)	Study Visit #4
Time Window		After completion of all screening	Day after completion of Baseline Headache logs	Within 1 week of completing headache logs	Day after Study Visit #2	> 7 days after starting, but still on medication	Within 7 days of 28 th day of Phase 2 monitoring	After Study Visit #3	Within 7 days of 56 th day of continued access phase meds
Meet Study Investigator/ Coordinator	Yes			Yes			Yes		Yes
Sign Consent	Yes								
Transcranial Doppler Exam	Yes								
Complete Quality of Life Survey	Yes						Yes		Yes
Blood Testing	Yes					Yes			
Receive Daily Reminder		Yes			Yes			Yes	
Record Daily Headache Log		Yes			Yes			Yes	
Receive Study Medication				Yes			Yes (if continuing)		
Take Study Drug					Yes			Yes	
Coordinator Reviews logs for compliance		Yes			Yes			Yes	
Coordinator Reviews Logs and Contacts Participant			Yes				Yes		Yes
Clinical Research Forms to be completed during visit (see Appendix 1)	Form 2-7	Form 8, 9 (if R to L shunt proven by TCD)	Form 10 (daily)	--	Form 11	Form 10 (Daily)	Complete Form 9 (PRU Result)	Form 12	Form 10 (Daily)
